Twenty (N=20) individuals at University of British Columbia with physician diagnosed T1D (N=10) or T2D (N=10) (HbA1c 6.5-8.5%), between the ages of 18-75 years, with a BMI between 25-40 kg/m² will be recruited through online social media and newspaper advertising.

Inclusion criteria will be: i) physician-diagnosed T1D or T2D of ≥1 year; ii) current HbA1c of 6.5-8.5%; iii) BMI: 25-40 kg/m2; iv) blood pressure of <160/99 mm Hg assessed according to guidelines; v) non-smoking; vi) not on hormone

replacement therapy, corticosteroids, or anti-inflammatory medications; and vii) 18–75 years old. **Exclusion criteria will include** i) Are taking more than 2 glucose lowering medications; ii) Are ongoing medical treatment for diseases such as cancer, auto-immune or inflammatory disease, liver or kidney disorders; iii) Have allergy, intolerance or aversion to cocoa, stevia, erythritol, inulin, or any other dietary restrictions (e.g., vegan) that will prevent them from following the standardized study diets; iv) Are unable to follow remote guidance by internet or smartphone; v) Are unable to follow the controlled diet instructions; vi) Are unable to read or communicate in English.

Based on our previous studies ~55% of males and ~70% of females with T1D or T2D who volunteer will meet these eligibility criteria so we anticipate no recruitment issues. We will allow statins and anti-hypertensive medications if on a stable dose for 3 months because the majority of T2D patients are on at least one of these medications; excluding them would leave a small pool for recruitment and limit the generalizability of our findings. Interested participants will provide their e-mail to establish direct and individual communication with research team.

A double-blinded crossover pilot trial is proposed. Eligible participants will complete 2 experimental trials separated by approximately 2-7 days, consuming no-sugar dark chocolate from Ross Chocolates and a conventional dark chocolate bar.

Due to COVID-19 breakout, this study is proposed to be done remotely since participants belong to risk group and will probably maintain in quarantine for unpredictable time. Information and guidance for the trial will be done by email, telephone calls and Zoom meeting. RedCap-UBC will be used to manage information and deliver questionnaires. Participants will be recruited after completing an online Eligibility questionnaire.

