Participants will receive in their homes a box containing a OneTouch Verio IQ® kit Blood glucose monitoring system (OneTouch Verio IQ® meter, lancing device, sterile lancets, carrying case), glucose strips, alcohol swabs, 1 bar of Ross dark chocolate (34g each) and 1 bar of a conventional dark chocolate (34g each) and instructions on how to proceed during each trial. Chocolate bars will be identical and wrapped equally and labeled as A and B, by Ross Chocolates (prepared in the same mold and packaged identically) who are not involved in any other aspects of the study, allowing for blinding of research team and participants. Participants will complete two experimental trials: 1) consumption of 1 bar (34g) of Ross dark chocolate 2) consumption of 1 bar (34g) of conventional dark chocolate. The order of the bars will be randomized so there will be an equal chance of getting bar A or bar B first (similar to drawing a name out of a hat or flipping a coin). Participants will be advised to perform both trials on the exact same time of day, in the morning after an overnight fast, refraining from diabetic medications. They will be asked to register glucose levels before and after eating the chocolates. A OneTouch Verio

IQ® meter will be used to measure blood glucose. Time points will be as follows: before consumption, 15 min after, 30min after, 45min after, 60min after, 90min after, 120min after. Values will be registered on a Glucose Form and stored on the meter and sent to research team by email. Participants will then be asked to Complete Taste Test Questionnaire sent by RedCap link through e-mail.

Study Timeline:

Baseline Contact

On the initial contact, by a FIRST email, participants will be informed of the study and asked to complete a Health Screening Questionnaire and sign electronically an Informed Consent. After confirmation of eligibility and given consent, participants will receive a SECOND email with information on the study kit and asked to inform Research team when kit arrives. The kit will contain:

- Study Welcoming, Instructions and Responsibilities
- Glucose levels form
- OneTouch Verio IQ® kit Blood glucose monitoring system (OneTouch Verio IQ® meter, lancing device, sterile lancets, carrying case)
- Glucose strips
- Alcohol swabs
- 1 bar of dark chocolate A (34g each)
- 1 bar of dark chocolate B (34g each)

Once participants confirm study kit was received, they will get a THIRD email suggesting to start the protocol.

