Participants will choose 2 different days, one for Day 1 and one for Day 2 (2-7 days apart from each other) and perform the following protocol:

Day 1

- ✓ Measure glucose levels before chocolate consumption and write down value on Glucose levels form
- ✓ Consume 1 bar of dark chocolate (A or B) according to instructions from Research team after randomization

- ✓ Measure glucose levels after consumption (15 min, 30 min, 45 min, 60 min, 90 min, 120 min) and write down values on Glucose levels form
- ✓ Complete Taste Test Questionnaire sent to participant's e-mail

Day 2

- ✓ Measure glucose levels before chocolate consumption and write down value on Glucose levels form
- ✓ Consume 1 bar of dark chocolate (A or B) according to instructions from Research team after randomization
- ✓ Measure glucose levels after consumption (15 min, 30 min, 45 min, 60 min, 90 min, 120 min) and write down values on Glucose levels form
- ✓ Complete Taste Test Questionnaire sent to participant's e-mail
- ✓ Send photo of Glucose levels form by email

A Zoom meeting will be scheduled to guide participants with procedures in study if necessary.

Statistical Analysis

Changes in blood glucose across time between conditions will be analyzed with a linear mixed effects model including time, condition, and their interaction as fixed effects and participant ID and baseline glucose values as random effects. Area under the curve and incremental AUC will be calculated and analyzed by paired t-test.

Sample size

Sample size calculation for a within-between interaction with alpha of 0.05, power of 80%, and an expected moderate effect size (f=0.25) reveals a sample size of 12 is needed to detect a significant difference. To preserve power and enable potential sub-analyses of type 1 vs. type 2 diabetes we will aim to recruit 20 participants for this preliminary study.

Significance

The results of this study will help determine whether by consuming a dark chocolate bar sweetened with stevia, erythritol, and inulin will cause a blood glucose spike in people with diabetes (T1D and T2D). This information will provide high quality scientific evidence which will allow individuals with diabetes more food choices, helping them manage diabetes better.

OUTCOMES MEASUREMENTS AND METHODS

The primary outcome measure is plasma glucose levels following consumption of the dark chocolate bars. The taste of the chocolates will also be evaluated.

Glucose Monitoring

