A glucose monitoring device (OneTouch Verio IQ® kit Blood glucose monitoring system) will be used to measure blood glucose levels before and after consumption of chocolates. Following consumption, measurements will be taken 15 min after, 30 min after, 45 min after, 60 min after, 90 min after, and 120 min after. Values will be registered on a form, stored on the meter and sent to research team by email. All to be done at home with no displacement.

Taste Test Questionnaire

Questionnaire is included as attachments and will be sent as link from the RedCap platform.

Protection of Human Subjects

All participants will be given a unique study code, with all data and information gathered connected with this code. Only the PI will have access to the master list linking the codes with participant names. Participant information and data will be either stored in a locked filing cabinet, or on an internal UBC network drive accessed only through a dedicated LAN internet connection on a password protected computer in the PIs laboratory with Salto passcard access only to the members of the research lab.

REDCap will be used as project management, storage of information, sending questionnaires and processing results. The REDCap platform is a secure web application for building and managing research data collection instruments. The platform is specifically designed to support online or offline data capture for research studies. The REDCap platform runs on server infrastructure physically located in BC, Canada, at the UBC University Data Centre (UDC).

POTENTIAL PROBLEMS AND ALTERNATIVE STRATEGIES

Diet compliance: Since the study involves a minor modification to diet, we do not anticipate that any adverse events due to the interventions will be seen.

Blood sampling:

When compared to traditional wet blood and plasma collection using venipuncture, capillary blood sampling is safer and easier, so much so that nearly anyone can perform the procedure, mainly diabetes patients who are used to doing finger pricks for glucose levels. However, risks associated with the process of finger-stick blood draws are minimized by usage of sterile and disposable material as well as hygiene procedures. Participants will receive their own kit with sterile material and instructions on procedure.

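### Taste is rated after participants have read two hours of their own glucose values, so the rating is exposed to an avoidable cue and to recall; it could be collected straight after eating

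*Combined protocol and SAP*

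**What the plan says.** All references are to the combined protocol and SAP.

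- **Design and blinding (Research Method).** "A double-blinded crossover pilot trial is proposed". Blinding rests on bars of the same form and wrapping, coded A and B by the manufacturer, "allowing for blinding of research team and participants". Nothing is said about glucose readings as a possible cue.
- **Glucose schedule (Research Method).** "Time points will be as follows: before consumption, 15 min after, 30min after, 45min after, 60min after, 90min after, 120min after".
- **Taste, narrative (Research Method).** After the glucose times and the recording of values: "Participants will then be asked to Complete Taste Test Questionnaire sent by RedCap link through e-mail".
- **Taste, checklists (Study Timeline, Day 1 and Day 2).** On each day the item "Measure glucose levels after consumption (15 min, 30 min, 45 min, 60 min, 90 min, 120 min) and write down values on Glucose levels form" comes first, followed by "Complete Taste Test Questionnaire sent to" the participant's e-mail address.
- **Status of taste (OUTCOMES MEASUREMENTS AND METHODS).** After naming glucose as primary: "The taste of the chocolates will also be evaluated". The Statistical Analysis section does not mention taste.
- **Instrument (Taste Test Questionnaire).** "Questionnaire is included as attachments and will be sent as link from the RedCap platform". The attachment is not part of the documents available.

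**The concern.** Taste is the only outcome named besides glucose, and it is a self-report. Such a rating is most credible when the person giving it has no outside information about which product was eaten and gives it while the experience is fresh. The written order works against both conditions. Participants rate the bar after following their own glucose for two hours. Someone who has just seen a flat or a rising curve may form a view of which bar it was, and that view may colour the rating.

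What is at stake is the credibility of any taste comparison between the two bars. The section on informed consent and ethics discloses that the manufacturer partly funds the study and may gain commercially, which is a reason to keep a subjective comparison as clean as is practical.

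**Working it through.** The plan gives no figure for taste. Its only calculated figure is a sample size of 12 (recruitment target 20), which concerns glucose and has no bearing here. The check is therefore a reading of the sequence.

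1. **Order.** The narrative in Research Method and the two day checklists all place the questionnaire after the glucose series. Three places agree, so this is not a slip in one sentence.

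2. **Delay.** The readings are at 0, 15, 30, 45, 60, 90 and 120 minutes. If the questionnaire follows the last one, the rating comes at least 120 minutes after eating. No clock time or deadline is attached to the form, so the delay is inferred from the order and could be longer.

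3. **What the participant has seen.** There are 7 readings a day, 1 before and 7 − 1 = 6 after eating. Participants take them at home and write them on a form. No masking of the meter is described.

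4. **Whether the readings carry information.** The Background expects the sweetener blend to leave glucose largely unmoved, and the comparator is a conventional dark chocolate bar. If that expectation is right, the two curves differ. Participants have had diabetes for at least a year and, according to the section on blood sampling, are used to finger-prick testing. On Day 1 there is one curve and nothing to set it against. On Day 2 there are two, so the cue is stronger.

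5. **Whether the order is needed.** No passage gives a reason for the delay. The first reading after eating is at 15 minutes, and the form is an online link that can be opened at any time. A short form can therefore fit before that reading. One limit is that the plan does not say whether the 15 minutes run from the start or the end of eating, so the usable gap may be less than 15 minutes.

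6. **Reach.** The mixed model, the AUC comparisons and the sample size all concern glucose. None uses the taste rating.

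**The case against.** The strongest case on the other side has five parts.

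- **Unblinding is not shown.** Participants are not told which bar they ate, and the bars look alike. Readings taken fasting and without diabetes medication, in a mixed type 1 and type 2 group, may not identify a bar for any one person. How far the curves differ is the trial's own question. This stands. A reader might infer that the taste outcome is unblinded, but the documents contain nothing on what participants guess. They support a risk only.
- **The consequence is small.** Taste is in neither the objectives nor the hypothesis, and no test of it is planned. This stands and limits the point. A reader might infer that the trial's double-blind comparison as a whole is compromised by this order, but the order of the taste form does not touch the glucose outcome.
- **The size is unknown.** A reader might try to attach a false-positive rate for a taste difference. That would need a rating scale, a standard deviation, the share of participants swayed, a common direction of the shift and a chosen test. The documents give none of these, so no such figure is offered.
- **Unseen material may set the timing.** The kit includes written instructions, and the questionnaire is a separate attachment; either could specify when to rate. This is possible. The protocol's own text would still state the later order and would need aligning.
- **An earlier form is neither a full cure nor free.** Flavour may itself reveal the bar, and on Day 2 participants still remember the Day 1 curve. An unsupervised participant busy with a form might also take the 15-minute reading late, which would affect the primary outcome. Both points stand. Flavour, however, is what the questionnaire is meant to capture, whereas the same-day readings are an outside influence that can be removed. The timing risk can be met with a priority rule.

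**Conclusion.** The point holds in a limited form. As written, a subjective rating is collected after participants have read their own glucose series. It is therefore at risk of unblinding from those readings, more on Day 2 than on Day 1, and it depends on recall of about two hours. Both weaknesses are largely avoidable.

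The effect is confined to taste, a non-primary outcome with no stated analysis. No magnitude can be given without the questionnaire scale.

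The conclusion rests on three assumptions: that the listed order is the order followed, that the meter display is visible to the participant, and that the two bars give glucose responses different enough to serve as a hint. The first two follow from the text as it stands. The third is the plan's own expectation and has not been established.

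This is a worthwhile small improvement, not a flaw that threatens the trial's main result.

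**What to change.** On both days:

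- Move the taste questionnaire in the checklist to directly after the bar is finished and before the 15-minute reading.
- Send the REDCap link in advance so that it is ready to open.
- Reword the matching sentence in Research Method so that it gives the same order.
- State that the 15-minute finger-stick takes priority if the form is not finished.

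**Cost.** One checklist line moves on each day, one sentence is reworded, the priority statement is added and the link goes out earlier. No visit, sample or staff time is added, and no glucose time point changes. The downside is that a short form must be completed before the 15-minute reading, which is why the priority rule is needed.

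**What it does not do.** It removes the same-day readings as a cue and shortens the recall. It does not remove flavour as a cue or, on Day 2, the memory of the Day 1 curve. Label: cheap improvement.

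### The daily steps specify no record of which bar was eaten or whether it was finished, so a swapped order may go undetected and would reverse that participant's paired difference

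*Combined protocol and SAP*

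**What the plan says.** The kit list under Baseline Contact includes "1 bar of dark chocolate A (34g each") and "1 bar of dark chocolate B (34g each"), so both bars are in the home before the first session. The Research Method section describes them: "Chocolate bars will be identical and wrapped equally and labeled as A and B". It sets the order as follows: "The order of the bars will be randomized so there will be an equal chance of getting bar A or bar B first".

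Under Study Timeline, Day 1 and Day 2 carry the same consumption step: "Consume 1 bar of dark chocolate (A or B) according to instructions from Research team after randomization". The recording steps around it concern glucose. Before eating: "Measure glucose levels before chocolate consumption and write down value on Glucose levels form". Afterwards, at 15 to 120 minutes, the participant measures again and is to "write down values on Glucose levels form". A taste questionnaire follows each session. Day 2 alone adds "Send photo of Glucose levels form by email".

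A Zoom meeting is offered only where needed, and for guidance. The diet compliance paragraph, under potential problems, discusses adverse events and gives no adherence check. The Statistical Analysis section fits condition as a fixed effect and compares the areas under the curve by paired t-test. It does not say whether condition means the bar assigned or the bar eaten.

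**The concern.** The link between a glucose curve and a bar depends on an unsupervised participant opening the right one of two look-alike wrappers on the right day. The listed steps leave no trace of which one was opened. The meter memory and the glucose values do not identify the bar.

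There is one bar of each kind, so eating the wrong one first leaves only the other for the second day, and the swap is complete. If the data are then analysed by assigned order, that participant does not merely add noise but contributes the true difference with its sign reversed. In a trial of 20, one or two such cases noticeably shrink the estimated contrast between bars, and nothing in the result would show why.

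The amount eaten is a related but separate gap. An unfinished bar changes that day's exposure without reversing any sign.

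**Working it through.** **The plan's own figure.** The Sample size section gives 12 for a within-between interaction with alpha 0.05, power 80% and f = 0.25. The number of groups k, the number of measurements m and the correlation ρ are not stated. Using a noncentral F with λ = f²·N·m/(1 − ρ), df1 = (k − 1)(m − 1) and df2 = (N − k)(m − 1):

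- k = 2, m = 14 (2 bars × 7 times), ρ = 0.5, N = 12: λ = 0.0625 × 12 × 14/0.5 = 21, df 13 and 130, power 84%. The smallest N reaching 80% is 12.
- k = 2, m = 7, ρ = 0.7, N = 12: λ = 0.0625 × 12 × 7/0.3 = 17.5, df 6 and 60, power 86%.
- k = 2, m = 7, ρ = 0.5, N = 12: λ = 10.5, power 62%.

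So 12 can be reached under some unstated inputs. It does not by itself fix an effect size for the paired comparison, and two are used below.

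**Effect of a swap on the estimate.** Let d be the sugar-free minus conventional difference for one participant. A complete swap analysed by assigned order turns d into −d. With s swaps among n participants:

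expected mean difference = [(n − s)·δ − s·δ]/n = δ·(1 − 2s/n)

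For n = 20 (the recruitment target) the multiplier is 0.90, 0.80 and 0.70 for s = 1, 2 and 3.

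**Effect on power.** Two-sided paired t-test at alpha 0.05 (two-sided is assumed; the plan does not say), simulated with 200,000 replicates and normal differences with unit SD, with s of the n differences sign-reversed. The standardised paired difference dz is an assumption: 0.66 gives 80% power at n = 20 without swaps, and 0.89 gives 80% at n = 12, the plan's calculated size.

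| n = 20 | 0 swaps | 1 | 2 | 3 |
|---|---|---|---|---|
| dz = 0.66 | 80% | 68% | 55% | 42% |
| dz = 0.89 | 96% | 90% | 78% | 62% |
| dz = 1.0 | 99% | 95% | 86% | 70% |

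**How likely is a swap?** The documents give no rate. If each participant swaps independently with probability p, the chance of at least one swap in 20 is 1 − (1 − p)^20: 33% for p = 2%, 64% for 5% and 88% for 10%. These rates are illustrations only.

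**Part-eaten bars.** Suppose, as the Background expects, that the sugar-free bar raises glucose less than the conventional bar. Leaving part of the conventional bar lowers the larger response and shrinks the contrast. Leaving part of the sugar-free bar lowers the smaller response or leaves it unchanged, so the contrast stays the same or widens. The direction therefore depends on which bar is left.

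**The case against.** The strongest reply is that the missing record may exist. The glucose form, the instruction sheet in the kit and the taste questionnaire are named but not reproduced, and any of them could carry an A/B or amount-eaten item. A reader might infer from the listed steps that a swap cannot be seen. The documents do not support that; they show only that the plan specifies no such record. Nor do they establish that the analysis must use the assigned order, since condition is left undefined. Both replies stand. The sign reversal is therefore conditional on a swap being missed and on analysis by assigned order.

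There are also mitigations. The bars carry distinct labels, guidance is given by email and telephone as well as Zoom, and people who cannot follow remote guidance or who have an aversion to the ingredients are excluded. These make swaps and leftovers less likely, but they do not record them.

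The power loss depends on the assumed effect. With dz = 0.89, one swap still leaves 90% at n = 20, and the plan recruits above its calculated size partly to protect power. That stands, and it is why a range is shown. The figures also concern the AUC t-test and not the mixed model.

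A further tempting inference is that swaps and unfinished bars both bias the trial towards its own hypothesis. This is not supported. An unfinished sugar-free bar need not shrink the contrast. The hypothesis wording is also ambiguous: the Background anticipates a lower or null spike for the sugar-free bar, and on that reading a swap works against the expected result.

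**Conclusion.** The concern holds in a limited form. The plan specifies no record of which bar was eaten or whether all of it was, in a home setting where both look-alike bars are present from the start. A swap may therefore go undetected. If it does, and the analysis follows the assigned order, each swap among 20 removes 10% of the expected mean difference. One to three swaps cost about 12 to 38 percentage points of power at dz = 0.66 (80% to 68% and to 42%) and about 6 to 34 points at dz = 0.89 (96% to 90% and to 62%).

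These sizes rest on an assumed number of swaps, an assumed paired effect and a two-sided test. The documents supply none of the three. For incomplete consumption, the direction of the effect depends on which bar is left.

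This is a gap in data capture, not proof of error in the result. It is worth closing because the information is nearly free to collect at the session and analysts cannot supply it afterwards.

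**What to change.** Unless the form already has them, add two items to the Day 1 and Day 2 steps and to the glucose form: the label (A or B) of the bar opened, and whether the whole bar was eaten, with the amount left if not. Where practicable, ask for a wrapper photo on each day. The current photo step is on Day 2 only and shows the form, so this needs either a second photo or the Day 1 wrapper to be kept. A wrapper confirms the label but not that the bar was finished, so the amount item is still needed.

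Before unblinding, define condition, state how deviations from the assigned order will be handled, and report results both as eaten and as assigned. Which of the two is primary is a matter of judgement for the trial team; the improvement does not depend on that choice.

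The cost is a few seconds per session, possibly one extra photo, and a short rule written in advance. The sample size and the intervention do not change, and recording A or B does not break the blind.

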Title: Impact of dark chocolate consumption on glucose levels of people with diabetes

Research Question: Does dark impact blood glucose levels in people with diabetes?

Objectives

- 1) To determine whether a dark chocolate sweetened with stevia, erythritol, and inulin compared to a standard dark chocolate bar impacts blood glucose levels in individuals with diabetes (T1D and T2D);
- 2) to understand and manage glucose levels in people with diabetes after consumption of different blends of chocolate.

Hypothesis:

a) A dark chocolate sweetened with stevia, erythritol, and inulin, compared to a standard dark chocolate bar will not impact blood glucose levels in individuals with diabetes (T1D and T2D)

Background Information

Diabetes is a growing concern in the world with an estimated 9.3% of adults, ages 20-79, with it in 2019, type 2 diabetes accounting for 90% of this total (1). In Canada, approximately 7.5% of adults have type 2 diabetes, 4.7% diagnosed and 2.8% undetected (2). Furthermore, an estimated 12.4% of adults in Canada have prediabetes, with 5-10% of those becoming diabetic each year (2). In order to prevent this, interventions aimed at weight loss, dietary change, and increased physical activity have been found to be effective (3). Additionally, a common recommendation for individuals with type 2 diabetes is to limit sugars and sweets as it may cause a high blood glucose response (4).

In diabetes, the postprandial phase is characterized by a rapid and large increase in blood glucose levels, and the possibility that these postprandial "hyperglycemic spikes" may be relevant to the pathophysiology of late diabetes complications is recently receiving much attention (5).

Postprandial hyperglycemia is a major component of glucose toxicity at the cellular and tissue level. Acute elevations of glucose after nutrient ingestion are associated with a variety of glucose-mediated tissue defects, including oxidative stress, lipid peroxidation, and advanced glycation end products (AGEs) formation leading to endothelial dysfunction and inflammation (6). This state not only initiates the development of early microvascular and macrovascular complications, but it also can contribute to a rapid progression to diabetes by causing glucose toxicity in muscle and pancreatic beta cells. The effects of hyperglycemia are often irreversible and lead to cell dysfunction.

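### With baseline glucose listed as a random effect and no visit-within-participant term, the model understates the standard error of the condition main effect if glucose level varies between visits beyond what baseline explains, unless each visit has its own baseline label

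*Combined protocol and SAP*

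**What the plan says.** All references are to the combined protocol and SAP.

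- **Model (Statistical Analysis).** The purpose of the model comes first: "Changes in blood glucose across time between conditions will be analyzed with a linear mixed effects model". The same sentence then sets out which terms enter it, and how: "including time, condition, and their interaction as fixed effects and participant ID and baseline glucose values as random effects". AUC and incremental AUC are analysed separately by paired t-test. No visit-level random effect, within-visit covariance or degrees-of-freedom method is given, here or elsewhere.
- **Design (Research Method).** "Eligible participants will complete 2 experimental trials separated by approximately 2-7 days". Order is randomised: "The order of the bars will be randomized so there will be an equal chance of getting bar A or bar B first".
- **Baseline (Study Timeline).** The instruction "Measure glucose levels before chocolate consumption and write down value on Glucose levels form" appears under both Day 1 and Day 2, so every visit has its own value. Six readings follow, from 15 to 120 minutes.
- **Question and outcome.** Objective 1 asks whether "a dark chocolate sweetened with stevia, erythritol, and inulin compared to a standard dark chocolate bar impacts blood glucose levels". The outcomes section says: "The primary outcome measure is plasma glucose levels following consumption of the dark chocolate bars". Neither names a time point or a model contrast.

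**The concern.** Within a participant, condition and visit coincide: one bar, one visit. The bar difference averaged over time therefore carries whatever made that person's glucose run high or low on that day. A participant intercept cancels in the comparison of bars and cannot represent this day-to-day variation. Unless another term does, the model treats the six readings of a visit as independent evidence.

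Baseline glucose is a continuous measurement, and calling it a random effect does not settle which model is fitted. The sentence can be read as:

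1. a fixed covariate, loosely labelled random, with a participant intercept only;
2. a slope on baseline that varies by participant;
3. one common random coefficient;
4. a grouping label made from the rounded value, which different participants can share;
5. a grouping label that happens to be unique to every visit.

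Readings 1 to 4 leave some visit variation in the residual. Reading 5 is equivalent to a visit-within-participant intercept, so its standard error is right, but it makes no baseline adjustment. What is at stake is that ordinary day-to-day variation could be declared a difference between bars in the condition term, while the planned t-tests on the same data say otherwise and no rule decides between them.

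**Working it through.** **The plan's own figure.** The plan gives no variance or standard error for this contrast. Its only figure is the sample size of 12 for a within-between interaction. That can be reached with 2 groups, 14 readings and correlation 0.5 (power 0.838), or 2 groups, 7 readings and correlation 0.7 (power 0.864). None of these inputs is stated, and the point below does not depend on them.

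**Inputs.** From the documents: 20 participants, 2 visits, 6 post-bar readings per visit, alpha 0.05. Not in the documents: any SD. Let s² be the single-reading variance, w² the visit variance left after baseline adjustment, and k = w²/s².

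**Closed form for a participant intercept and no visit term.**

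- True variance of the time-averaged bar difference: (2/20)(w² + s²/6).
- Residual degrees of freedom: 19 × 2 × 5 = 190 within visits, and 19 − 1 = 18 at visit level after the baseline coefficient; 208 in all.
- Expected residual variance: [190s² + 18(s² + 6w²)]/208 = s²(1 + 108k/208) = s²(1 + 0.52k).
- Variance the model reports: (2/20)(s²/6)(1 + 0.52k).
- Model SE / true SD = √[(1 + 0.52k)/(1 + 6k)].
- False-positive rate: P(|Z| > 2.093 × ratio), where 2.093 is the critical value of t on 19 df, which is lenient to the plan.

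| k (assumed) | SE ratio | False-positive rate |
|---|---|---|
| 0.05 | 0.89 | 6% |
| 0.1 | 0.81 | 9% |
| 0.25 | 0.67 | 16% |
| 0.5 | 0.56 | 24% |
| 1 | 0.47 | 33% |
| 2 | 0.40 | 41% |
| very large | 0.29 | 54% |

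With 208 df in place of 19, k from 0.05 to 2 gives 8-44%. At k = 0 the ratio is 1 and there is no inflation.

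**Simulation of each reading.** REML, 2000 null trials per scenario, 20 participants. Assumed: participant SD 2, reading SD 0.6, mean fasting glucose 8 mmol/L. Seven variance sets were used: visit SD 0.3, 0.5, 1.0 and 1.5; visit SD 1 with an extra visit-level response SD of 0.6; visit SD 1 with serial correlation 0.6 per 15 minutes; and visit SD 0.3 with response SD 0.6. Rejection of the condition term on 19 df (17 df in the last row):

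| Reading of baseline | Range |
|---|---|
| 1. Fixed covariate, participant intercept only | 0.193-0.395 |
| 2. Slope by participant | 0.147-0.399 |
| 3. Common random coefficient | 0.191-0.389 |
| 4. Label rounded to 0.1 mmol/L | 0.074-0.251 |
| 4. Label rounded to 1 mg/dL | 0.070-0.173 |
| 5. Label unique to each visit | 0.040-0.056 |
| Visit intercept, split baseline, period | 0.044-0.051 |

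**Two sources in readings 1 to 3.** One coefficient shared between and within participants is pulled towards the between-participant slope and over-corrects a noisy fasting reading. At visit SD 0.3, a participant-intercept model rejects 0.193 with a shared coefficient but 0.129 when fasting glucose is split into participant mean and visit deviation. With the split, k = v²/(v² + 0.36) for visit SD v, so k = 0.09/0.45 = 0.20 at v = 0.3 and 1/1.36 = 0.74 at v = 1. The closed form then predicts 0.138 and 0.29, against 0.129 and 0.290 simulated. At visit SD 0, separate runs of reading 1 gave between about 4% and 11%; the excess there is the shared coefficient alone. Reading 4 gave about 3%.

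**Cross-check with time 0 kept as an outcome (7 readings).** Assumed reading SD 1.0, baseline absorbing nothing, visit SD sv. Correct SE: √[2(sv² + 1/7)/20]. Residual variance: 1 + (19 × 7/247)sv² = 1 + 0.538sv². The model SE is 0.127 against 0.198 at sv 0.5 (ratio 0.64), 0.148 against 0.338 at 1.0 (0.44), and about 0.177 against 0.489 at 1.5 (0.36).

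**The other planned tests.** Time-by-condition rejects 0.001-0.052 without serial correlation. In the 7-reading layout its SE is too large, by √1.538 = 1.24 at sv 1.0. With serial correlation it rejects 0.011-0.049 under readings 1 to 3 and 0.075 under reading 4. Reading 5 also gives 0.075, so that excess is due to ignored serial correlation, not the baseline term. Paired t-tests reject 0.038-0.054 (AUC) and 0.043-0.057 (net incremental AUC).

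**The case against.** The strongest reply is that the affected test may not be the one the trial relies on. The model sentence speaks of change over time between conditions, and the sample size is for an interaction; that test is not inflated. AUC is close to a time-average, and its paired t-test uses one value per visit. This stands, and it limits the harm to a condition term that nobody has yet said will be the answer. It does not remove the point: the model does produce that term, Objective 1 reads as an overall comparison of bars, and no contrast is named as primary.

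Second, the most literal reading is two grouping factors, where the rates are 7-25% or nominal. This also stands, so the 15-40% figures should not be quoted as the plan's error rate. They matter because the covariate reading is the natural one for a continuous baseline, and merely relabelling it as fixed would not supply the visit term.

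Third, the visit variance is unknown. True; if baseline absorbed it all, the main mechanism would vanish. But these are fasting home tests on days the participants choose, with diabetic medication withheld, and the visit term costs little if the variance is near zero.

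A reader might infer that the trial's principal test is invalid, or that its sample size is wrong for this reason. The documents support neither: they name no principal contrast, the interaction and t-tests hold up, and the sample-size calculation is a separate matter.

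**Conclusion.** Wrong as written, with limited reach. The sentence specifies no term that reliably carries visit-to-visit variation, and four of five plausible ways of fitting it understate the standard error of the condition main effect when such variation remains after baseline. The fifth gets the standard error right but forgoes baseline adjustment. The size cannot be derived from the documents: the simulated rates rest on assumed visit SDs of 0.3-1.5 mmol/L and the other SDs listed, and they are not upper bounds. Part of the inflation under the covariate and slope readings belongs to the shared baseline coefficient, not to the missing visit term. The consequence is real only if the condition term is reported as the answer to Objective 1; nothing in the plan prevents that, and nothing says which result counts if it conflicts with the t-tests.

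**What to change.** Replace the model sentence with text that does the following:

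- **Baseline.** Enter each visit's fasting glucose as a fixed covariate, and exclude time 0 from the outcome. Preferably split it into the participant's mean over both visits and that visit's deviation from it. In the simulations the split reduced the SD of the bar difference from 0.188 to 0.117 mmol/L at visit SD 0.3, and made almost no difference at 1.5 (0.195 against 0.198).
- **Random effects.** Intercepts for participant and for visit within participant.
- **Degrees of freedom.** Test the condition term on visit-level degrees of freedom, about 17-19, not on the number of readings: 20 − 1 = 19, less one for the fasting deviation, less one more if period is included.
- **Primary contrast.** State whether it is the time-averaged bar difference, time-by-condition, or another contrast. The choice is the sponsor's. Once time 0 is only a covariate, a bar effect equal at all six times appears in the condition term alone.
- **Paired t-tests.** Keep both, and say how they rank against the model.

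A period term and a serial-correlation structure are optional. The simulated model had a visit intercept, split baseline and period, tested on 17 df; no serial-correlation structure was fitted.

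Cost: a few sentences and one or two degrees of freedom. No new data.
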